Grade 0 - none Grade 1 - mild Grade 2 - moderate Grade 3 - severe TREF 3.11: Comparison of Systemic Reaction at Post Immunization each Follow up Time by GPO Tri fluvac and Active Comparator Group

	30 min.		Day 1		Day 2		Day 3	
Systemic Reaction	Tri	Comparator	Tri fluvac	Comparator	Tri fluvac	Comparator	Tri fluvac	Comparator
	fluvac	(N=xx)						
- Headache, n (%)	xx(xx.xx)	xx(xx.xx)						
p-value =	Х	X.XXXX						
- Fatigue, n (%)								
p-value =								
- Malaise, n (%)								
p-value =								
- Chills, n (%)								
p-value =								
- Myalgia, n (%)								
p-value =								
- Arthralgia, n (%)								
p-value =								
- Nausea, n (%)								
p-value =								
- Vomiting, n (%)								
p-value =								
- Rash, n (%)								
p-value =								

Note: Summary by case who had symptoms

Systemic I	Reaction	Tri fluvac	Comparator
		(N=XX)	(N=XX)
Headache,	n (%)		
Grade 0		XX(XX.XX)	xx(xx.xx)
Grade 1		xx(xx.xx)	xx(xx.xx)
Grade 2		XX(XX.XX)	XX(XX.XX)
Grade 3		XX(XX.XX)	XX(XX.XX)
	p-value = x	XXXX	
Fatigue, n (%)		
Grade 0			
Grade 1			
Grade 2			
Grade 3			
	p-value =		
Malaise, n ((%)		
Grade 0			
Grade 1			
Grade 2			
Grade 3			
	p-value =		
Chills, n (%	ы 1		
Grade 0	•)		
Grade 1			
Grade 2			
Grade 3			
	p-value =		
Myaloia n	(%)		
Grada 0	(70)		
Grade 1			
Grade 1			
Grade 2			
Glade 5	n-value =		
Authualais	p-value -		
Arturaigia,	ш (%)		
Grade 0			
Grade 1			
Grade 2			
Grade 3			
	p-value =		

TREF 3.12: Comparison of Maximum Grade of Systemic Reaction by Symptom at Post Immunization by GPO Tri fluvac and Active Comparator Group

Systemic Reaction	Tri fluvac (N=xx)	Comparator (N=xx)
Nausea, n (%)		
Grade 0	XX(XX.XX)	xx(xx.xx)
Grade 1	xx(xx.xx)	xx(xx.xx)
Grade 2	XX(XX.XX)	xx(xx.xx)
Grade 3	XX(XX.XX)	xx(xx.xx)
p-value =		
Vomiting, n (%)		
Grade 0		
Grade 1		
Grade 2		
Grade 3		
p-value =		
Rash, n (%)		
Grade 0		
Grade 1		
Grade 2		
Grade 3		
p-value =		

TREF 3.12: Comparison of Maximum Grade of Systemic Reaction by Symptom at Post Immunization by GPO Tri fluvac and Active Comparator Group (Continue)

- Note: On any day (by cases)
 - Grading
 - Grade 0 none Grade 1 - mild Grade 2 - moderate Grade 3 - severe

Number of Days by Systemic Reaction		ion Tri fluvac	Comparator
Haadaaba	only 20 min	(IN-XX)	(N-XX)
пеацасце	omy 50 mm.		XX(XX.XX)
		XX(XX.XX) XX(VX XX)	XX(XX.XX) XX(XX.XX)
	2 days	•••(••••••)	лл(лл.лл) vv(vv vv)
	3 days	~~~~~~~~~~~~~~~~~~~~~~~~~~~~~~~~~~~~~~	лл(лл.лл) vv(vv vv)
	4 days		XX(XX.XX)
	5 days	XX(XX.XX)	XX(XX.XX)
	p-value =	X.XXXX	
Fatigue	only 30 min.		
	1 day		
	2 days		
	3 days		
	4 days		
	5 days		
	p-value =	X.XXXX	
Malaise	only 30 min.		
	1 day		
	2 days		
	3 days		
	4 days		
	5 days		
	p-value =	X.XXXX	
Chills	only 30 min.		
	1 day		
	2 days		
	3 days		
	4 days		
	5 days		
	p-value =	X.XXXX	
Myalgia	only 30 min.		
	1 day		
	2 days		
	3 days		
	4 days		
	5 days		
	p-value =	X.XXXX	

TREF 3.13: Comparison Number of Subject by Number of Systemic Reaction Days at Post Immunization GPO Tri fluvac and Active Comparator Group

Number of Days by Systemic Reaction		Tri fluvac (N=xx)	Comparator (N=xx)	
Arthralgia	only 30 min.	XX(XX.XX)	XX(XX.XX)	
	1 day	xx(xx.xx)	xx(xx.xx)	
	2 days	xx(xx.xx)	xx(xx.xx)	
	3 days	xx(xx.xx)	xx(xx.xx)	
4 days		xx(xx.xx)	xx(xx.xx)	
	5 days	xx(xx.xx)	xx(xx.xx)	
p-value = x.xxxx				
Nausea	only 30 min.			
	1 day			
	2 days			
	3 days			
	4 days			
	5 days			
	p-value = x.xxxx			
Vomiting	only 30 min.			
	1 day			
	2 days			
	3 days			
	4 days			
	5 days			
	p-value = x.xxxx			
Rash	only 30 min.			
	1 day			
	2 days			
	3 days			
	4 days			
	5 days			
	p-value = x.xxxx			

TREF 3.13: Comparison Number of Subject by Number of Systemic Reaction Days at Post Immunization between GPO Tri fluvac and Active Comparator Group (Continue)

Note: - Subjects who had symptom with Systemic reaction will be considered in this table.

- Number of subjects who had symptom will be compared between Tri fluvac and comparator.

- Percentage will be calculated from total enrollment subjects.

Number of Local Reaction	Tri fluvac (N=xx)	Comparator (N=xx)	
No symptom	xx(xx.xx)	xx(xx.xx)	
1 symptom	xx(xx.xx)	xx(xx.xx)	
2 symptoms	xx(xx.xx)	XX(XX.XX)	
3 symptoms	xx(xx.xx)	xx(xx.xx)	
4 symptoms	xx(xx.xx)	xx(xx.xx)	
5 symptoms	xx(xx.xx)	xx(xx.xx)	
6 symptoms	xx(xx.xx)	xx(xx.xx)	
7 symptoms	xx(xx.xx)	xx(xx.xx)	
8 symptoms	xx(xx.xx)	xx(xx.xx)	
9 symptoms	xx(xx.xx)	xx(xx.xx)	

TREF 3.14: Comparison Number of Subjects by Number of Systemic Reaction at Post Immunization between GPO Tri fluvac and Active Comparator Group

Note: - All enrollment Subjects will be considered in this table.

- Percentage will be calculated from total enrollment subject.

4. Immunogenicity

TREF 4.1: Comparing Seroconversion Rates between GPO Tri fluvac and Active Comparator Group Separated by HI Assay at Day 21 and 90

TREF 4.2: Comparing Seroconversion Rates between GPO Tri fluvac and Active Comparator at Any Day

TREF 4.3: Comparing Seroconversion Rates Separated by HI Assay at Day 21 and 90 in Sub-Group Pre-Vaccination HI Antibody titer < 1:10

TREF 4.4: Comparing Seroconversion Rates Separated by HI Assay at Day 21 and 90 in Sub-Group Pre-Vaccination HI Antibody titer $\geq 1:10$

TREF 4.5: Comparing Seroprotective Rates between GPO Tri fluvac and Active Comparator Group Separated by HI Assay at Day 21 and 90

TREF 4.6: Comparing Seroprotective Rates Separated by HI Assay at Day 21 and 90 in Sub-Group Pre-Vaccination HI Antibody titer < 1:10

TREF 4.7: Comparing Seroprotective Rates Separated by HI Assay at Day 21 and 90 in Sub-Group Pre-Vaccination HI Antibody titer $\geq 1:10$

TREF 4.8: Geometric Mean Titer (GMTs) of Immune Response by GPO Tri fluvac and Active Comparator Group

TREF 4.9: Geometric Mean Titer (GMTs) of Immune Response by GPO Tri fluvac and Active Comparator Group in Sub-Group Pre-Vaccination HI Antibody Titer < 1:10

TREF 4.10: Geometric Mean Titer (GMTs) of Immune Response by GPO Tri fluvac and Active Comparator Group in Sub-Group Pre-Vaccination HI Antibody Titer \geq 1:10

TREF 4.11: Geometric Mean Fold Rises (GMFRs) of Immune Response by GPO Tri fluvac and Active Comparator Group

TREF 4.12: Geometric Mean Fold Rises (GMFRs) of Immune Response by GPO Tri fluvac and Active Comparator Group in Sub-Group Pre-Vaccination HI Antibody Titer < 1:10

TREF 4.13: Geometric Mean Fold Rises (GMFRs) of Immune Response by GPO Tri fluvac and Active Comparator Group in Sub-Group Pre-Vaccination HI Antibody Titer \geq 1:10

HI Assay	Follow up Day	Study Group	4- fold rising n (%)	Not 4 -fold n (%)		
Flu A H1	Day 21	Tri fluvac (N=xx)	xx(xx.xx)	xx(xx.xx)		
		Comparator (N=xx)	xx(xx.xx)	xx(xx.xx)		
		p - value = x.xxxx				
	D ay 90	Tri fluvac (N=xx)				
		Comparator (N=xx)				
		p - value =				
Flu A H3	Day 21	Tri fluvac (N=xx)	xx(xx.xx)	xx(xx.xx)		
		Comparator (N=xx)	xx(xx.xx)	xx(xx.xx)		
		p - value = x.xxxx				
	D ay 90	Tri fluvac (N=xx)				
		Comparator (N=xx)				
		p - value =				
Flu B	Day 21	Tri fluvac (N=xx)	xx(xx.xx)	xx(xx.xx)		
		Comparator (N=xx)	xx(xx.xx)	xx(xx.xx)		
		p - value = x.xxxx				
	D ay 90	Tri fluvac (N=xx)				
		Comparator (N=xx)				
		p - value =				

TREF 4.1: Comparing Seroconversion Rates between GPO Tri fluvac and Active Comparator Group Separated by HI Assay at Day 21 and 90

Note: Enrollment cases will be compared between GPO Tri fluvac and Active Comparator Group.
HAI Assay	Study Group	4- fold rising n (%)	Not 4 -fold n (%)
H1 Antibody Titer	Tri fluvac $(N = xx)$ Comparator $(N = xx)$ p - value = x.xxxx	xx.xx(xx.xx) xx.xx(xx.xx)	xx.xx(xx.xx) xx.xx(xx.xx)
H3 Antibody Titer	Tri fluvac $(N = xx)$ Comparator $(N = xx)$ p - value =		
Flu B Antibody Titer	Tri fluvac $(N = xx)$ Comparator $(N = xx)$ p - value =		

TREF 4.2: Comparing Seroconversion Rates between GPO Tri fluvac and Active Comparator at Any Day

HI Assay	Follow up Day	Study Group	4- fold rising n (%)	Not 4 -fold n (%)
Flu A H1	Day 21	Tri fluvac (N=xx)	xx(xx.xx)	xx(xx.xx)
		Comparator (N=xx)	xx(xx.xx)	xx(xx.xx)
		p - value = x.	XXXX	
	Day 90	Tri fluvac (N=xx)	xx(xx.xx)	xx(xx.xx)
		Comparator (N=xx)	xx(xx.xx)	xx(xx.xx)
		p - value = x.	XXXX	
Flu A H3	Day 21	Tri fluvac (N=xx)		
		Comparator (N=xx)		
		p - value =		
	Day 90	Tri fluvac (N=xx)		
		Comparator (N=xx)		
		p - value =		
Flu B	Day 21	Tri fluvac (N=xx)		
		Comparator (N=xx)		
		p - value =		
	Day 90	Tri fluvac (N=xx)		
		Comparator (N=xx)		
		p - value =		

TREF 4.3: Comparing Seroconversion Rates Separated by HI Assay at Day 21 and 90 in Sub – Group Pre-Vaccination HI Antibody titer < 1:10

Note: Enrollment cases will be compared between GPO Tri fluvac and Active Comparator Group.

HI Assay	Follow up Day	Study Gi	roup	4- fold rising n (%)	Not 4 -fold n (%)
Flu A H1	Day 21	Tri fluvac	(N=xx)	xx(xx.xx)	xx(xx.xx)
		Comparato	r (N=xx)	xx(xx.xx)	xx(xx.xx)
			p - value = x.xxxx		
	Day 90	Tri fluvac	(N=xx)		
		Comparato	r (N=xx)		
			p - value =		
Flu A H3	Day 21	Tri fluvac	(N=xx)	xx(xx.xx)	xx(xx.xx)
		Comparato	r (N=xx)	xx(xx.xx)	xx(xx.xx)
			p - value = x.xxxx		
	Day 90	Tri fluvac	(N=xx)		
		Comparato	r (N=xx)		
			p - value =		
Flu B	Day 21	Tri fluvac	(N=xx)	xx(xx.xx)	xx(xx.xx)
		Comparato	r (N=xx)	xx(xx.xx)	xx(xx.xx)
			p - value = x.xxxx		
	Day 90	Tri fluvac	(N=xx)		
		Comparato	r (N=xx)		
			p - value =		

TREF 4.4: Comparing Seroconversion Rates Separated by HI Assay at Day 21 and 90 in Sub-Group Pre-Vaccination HI Antibody titer ≥ 1:10

Note: Enrollment cases will be compared between GPO Tri fluvac and Active Comparator Group.

HI Assay	Follow up Day	Study Group	Seroprotective n (%)	Non-seroprotective n (%)
Flu A H1	Day 21	Tri fluvac (N=xx)	xx(xx.xx)	xx(xx.xx)
		Comparator (N=xx)	xx(xx.xx)	xx(xx.xx)
		p - value = x.xxx	XX	
	Day 90	Tri fluvac (N=xx)		
		Comparator (N=xx)		
		p - value =		
Flu A H3	Day 21	Tri fluvac (N=xx)	xx(xx.xx)	xx(xx.xx)
		Comparator (N=xx)	xx(xx.xx)	xx(xx.xx)
		p - value = x.xxx	XX	
	Day 90	Tri fluvac (N=xx)		
		Comparator (N=xx)		
		p - value =		
Flu B	Day 21	Tri fluvac (N=xx)	xx(xx.xx)	xx(xx.xx)
		Comparator (N=xx)	xx(xx.xx)	xx(xx.xx)
		p - value = x.xxx	xx	
	Day 90	Tri fluvac (N=xx)		
		Comparator (N=xx)		
		p - value =		

TREF 4.5: Comparing Seroprotective Rates between GPO Tri fluvac and Active Comparator Group Separated by HI Assay at Day 21 and 90

Note: - Enrollment cases will be compared between GPO Tri fluvac and Active Comparator Group.

- Seroprotective level: HI antibody titer \geq 1:40

HI Assay	Follow up Day	Study Group	Seroprotective n (%)	Non-seroprotective n (%)
Flu A H1	Day 21	Tri fluvac (N=xx)	xx(xx.xx)	xx(xx.xx)
		Comparator (N=xx)	xx(xx.xx)	xx(xx.xx)
		p - value = x.xxx	xx	
	Day 90	Tri fluvac (N=xx)		
		Comparator (N=xx)		
		p - value =		
Flu A H3	Day 21	Tri fluvac (N=xx)	xx(xx.xx)	xx(xx.xx)
		Comparator (N=xx)	xx(xx.xx)	xx(xx.xx)
		p - value = x.xxx	(X	
	Day 90	Tri fluvac (N=xx)		
		Comparator (N=xx)		
		p - value =		
Flu B	Day 21	Tri fluvac (N=xx)	xx(xx.xx)	xx(xx.xx)
		Comparator (N=xx)	xx(xx.xx)	xx(xx.xx)
		p - value = x.xxx	XX	
	Day 90	Tri fluvac (N=xx)		
		Comparator (N=xx)		
		p - value =		

TREF 4.6: Comparing Seroprotective Rates Separated by HI Assay at Day 21 and 90 in Sub-Group Pre-Vaccination HI Antibody titer < 1:10

HI Assay	Follow up Day	Study Grou	þ	Seroprotective n (%)	Non-seroprotective n (%)
Flu A H1	Day 21	Tri fluvac (N=	xx)	xx(xx.xx)	xx(xx.xx)
		Comparator (N=	xx)	xx(xx.xx)	xx(xx.xx)
		p - val	ue = x.xxxx		
	Day 90	Tri fluvac (N=	xx)		
		Comparator (N=	xx)		
		p - val	ue =		
Flu A H3	Day 21	Tri fluvac (N=	xx)	xx(xx.xx)	xx(xx.xx)
		Comparator (N=	xx)	xx(xx.xx)	xx(xx.xx)
		p - val	ue = x.xxxx		
	Day 90	Tri fluvac (N=	xx)		
		Comparator (N=	xx)		
		p - val	ue =		
Flu B	Day 21	Tri fluvac (N=	xx)	xx(xx.xx)	xx(xx.xx)
		Comparator (N=	xx)	xx(xx.xx)	xx(xx.xx)
		p - val	ue = x.xxxx		
	Day 90	Tri fluvac (N=	xx)		
		Comparator (N=	xx)		
		p - val	ue =		

TREF 4.7: Comparing Seroprotective Rates Separated by HI Assay at Day 21 and 90 in Sub-Group Pre-Vaccination HI Antibody titer ≥ 1:10

HAI Assay	Day 0 GMT(95% CI)	Day 21 GMT(95% CI)	Day 90 GMT(95% CI)
Flu A H1 Antibody titer			
Tri fluvac	xx.xx(xx.xx - xx.xx)	xx.xx(xx.xx - xx.xx)	xx.xx(xx.xx - xx.xx)
Comparator	xx.xx(xx.xx - xx.xx)	xx.xx(xx.xx - xx.xx)	xx.xx(xx.xx - xx.xx)
P - value	= x.xxxx	X.XXXX	X.XXXX
Flu A H3 Antibody titer			
Tri fluvac			
Comparator			
P - value	=		
Flu B Antibody titer			
Tri fluvac			
Comparator			
P - value	=		

TREF 4.8: Geometric Mean Titer (GMTs) of Immune Response by GPO Tri fluvac and Active Comparator Group

Note: Enrollment cases will be compared between GPO Tri fluvac and Active Comparator.

HAI Assay	Day 0 GMT(95% CI)	Day 21 GMT(95% CI)	Day 90 GMT(95% CI)
Flu A H1 Antibody tit	er		
Tri fluvac	xx.xx(xx.xx - xx.xx)	xx.xx(xx.xx - xx.xx)	xx.xx(xx.xx - xx.xx)
Comparator	xx.xx(xx.xx - xx.xx)	xx.xx(xx.xx - xx.xx)	xx.xx(xx.xx - xx.xx)
P - valu	ie = x.xxxx	X.XXXX	X.XXXX
Flu A H3 Antibody tit	er		
Tri fluvac			
Comparator			
P - valu	ie =		
Flu B Antibody titer			
Tri fluvac			
Comparator			
P - valu	ie =		

TREF 4.9: Geometric Mean Titer (GMTs) of Immune Response by GPO Tri fluvac and Active Comparator Group in Sub-Group Pre-Vaccination HI Antibody Titer < 1:10

Note: - Enrollment cases will be compared between GPO Tri fluvac and Active Comparator. - † For titer reported as < 10, a value of 5 will be assigned when computing GMT

HAI A	ssay	Day 0 GMT(95% CI)	Day 21 GMT(95% CI)	Day 90 GMT(95% CI)
Flu A H1 Ant	ibody titer			
Tri fluvac		xx.xx(xx.xx - xx.xx)	xx.xx(xx.xx - xx.xx)	xx.xx(xx.xx - xx.xx)
Comparator		xx.xx(xx.xx - xx.xx)	xx.xx(xx.xx - xx.xx)	xx.xx(xx.xx - xx.xx)
	P - value =	x.xxxx	X.XXXX	X.XXXX
Flu A H3 Ant	ibody titer			
Tri fluvac				
Comparator				
	P - value =			
Flu B Antibod	ly titer			
Tri fluvac				
Comparator				
	P - value =			

TREF 4.10: Geometric Mean Titer (GMTs) of Immune Response by GPO Tri fluvac and Active Comparator Group in Sub-Group Pre-Vaccination HI Antibody Titer ≥ 1:10

Note: - Enrollment cases will be compared between GPO Tri fluvac and Active Comparator. - † For titer reported as < 10, a value of 5 will be assigned when computing GMT

	Tri fluvac	Comparator
HAI Assay	(N = xx)	(N = xx)
Flu A H1 antibody titer		
Day 0		
GMT [†] (95% CI)	xx.xx(xx.xx - xx.xx)	xx.xx(xx.xx - xx.xx)
Day 21		
GMT [†] (95% CI)	xx.xx(xx.xx - xx.xx)	xx.xx(xx.xx - xx.xx)
GMFRs	XX.XX	XX.XX
Day 90		
GMT [†] (95% CI)	xx.xx(xx.xx - xx.xx)	xx.xx(xx.xx - xx.xx)
GMFRs	XX.XX	XX.XX
Flu A H3 antibody titer		
Day 0		
GMT [†] (95% CI)		
Day 21		
GMT [†] (95% CI)		
GMFRs [‡]		
Day 90		
GMT [†] (95% CI)		
GMFRs [‡]		
Flu B antibody titer		
Day 0		
GMT [†] (95% CI)		
Day 21		
GMT [†] (95% CI)		
$\mathrm{GMFRs}^{\ddagger}$		
Day 90		
GMT [†] (95% CI)		
GMFRs [‡]		

TREF 4.11: Geometric Mean Fold Rises (GMFRs) of Immune Response by GPO Tri fluvac and Active Comparator Group

Note: - Enrollment cases will be compared between GPO Tri fluvac and Active Comparator.

- \dagger For titer reported as < 10, a value of 5 will be assigned when computing GMT; \ddagger GMFR is the geometric mean of the ratios of post - vaccination to the pre-vaccination

	Tri fluvac	Comparator
HAI Assay	(N = xx)	(N = xx)
Flu A H1 antibody titer		
Day 0		
GMT [†] (95% CI)	xx.xx(xx.xx - xx.xx)	xx.xx(xx.xx - xx.xx)
Day 21		
GMT [†] (95% CI)	xx.xx(xx.xx - xx.xx)	xx.xx(xx.xx - xx.xx)
GMFRs	XX.XX	XX.XX
Day 90		
GMT [†] (95% CI)	xx.xx(xx.xx - xx.xx)	xx.xx(xx.xx - xx.xx)
GMFRs	XX.XX	XX.XX
Flu A H3 antibody titer		
Day 0		
GMT [†] (95% CI)		
Day 21		
GMT [†] (95% CI)		
GMFRs [‡]		
Day 90		
GMT [†] (95% CI)		
GMFRs [‡]		
Flu B antibody titer		
Day 0		
GMT [†] (95% CI)		
Day 21		
GMT [†] (95% CI)		
$\mathrm{GMFRs}^{\ddagger}$		
Day 90		
GMT [†] (95% CI)		
G MFRs [‡]		

TREF 4.12: Geometric Mean Fold Rises (GMFRs) of Immune Response by GPO Tri fluvac and Active Comparator Group in Sub-Group Pre-Vaccination HI Antibody Titer < 1:10

Note: - Enrollment cases will be compared between GPO Tri fluvac and Active Comparator.

- \dagger For titer reported as < 10, a value of 5 will be assigned when computing GMT; \ddagger GMFR is the geometric mean of the ratios of post - vaccination to the pre-vaccination

HALA SSON	Tri fluvac	Comparator
ПАГАЗЗАУ	(N = xx)	(N = xx)
Flu A H1 antibody titer		
Day 0		
GMT [†] (95% CI)	xx.xx(xx.xx - xx.xx)	xx.xx(xx.xx - xx.xx)
Day 21		
GMT [†] (95% CI)	xx.xx(xx.xx - xx.xx)	xx.xx(xx.xx - xx.xx)
GMFRs	XX.XX	XX.XX
Day 90		
GMT [†] (95% CI)	xx.xx(xx.xx - xx.xx)	xx.xx(xx.xx - xx.xx)
GMFRs	XX.XX	XX.XX
Flu A H3 antibody titer		
Day 0		
GMT [†] (95% CI)		
Day 21		
GMT [†] (95% CI)		
GMFRs [‡]		
Day 90		
GMT [†] (95% CI)		
GMFRs [‡]		
Flu B antibody titer		
Day 0		
GMT [†] (95% CI)		
Day 21		
GMT [†] (95% CI)		
GMFRs [‡]		
Day 90		
GMT [†] (95% CI)		
GMFRs [‡]		

TREF 4.13: Geometric Mean Fold Rises (GMFRs) of Immune Response by GPO Tri fluvac and Active Comparator Group in Sub-Group Pre-Vaccination HI Antibody Titer ≥ 1:10

Note: - Enrollment cases will be compared between GPO Tri fluvac and Active Comparator.

- \dagger For titer reported as < 10, a value of 5 will be assigned when computing GMT; \ddagger GMFR is the geometric mean of the ratios of post - vaccination to the pre-vaccination

5. Concomitant Medication

TREF 5: Summary of Concomitant Medication According to WHO DD by GPO Tri fluvac and Active Comparator Group

TREF 5: Summary of Concomitant Medication According to WHO DD by GPO Tri fluvac and Active Comparator Group

		Number	of Event	Number of Case		
Anatomical Main Group	Therapeutic Subgroup	Tri fluvac (N=xx)	Comparator (N=xx)	Tri fluvac (N=xx)	Comparator (N=xx)	
		n (%)	n (%)	n (%)	n (%)	
XXXXXXXXX	XXXXXXXXX	xx (xx.xx)	xx (xx.xx)	xx (xx.xx)	xx (xx.xx)	
XXXXXXXXX	XXXXXXXX	xx (xx.xx)	xx (xx.xx)	xx (xx.xx)	xx (xx.xx)	

APPENDICES

Observe	Screening Number	Reason for Exclude
1		
2		
3		

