# **1. PROTOCOL SUMMARY**

Title:	A Phase II/III Double Blinded, Randomized, Controlled, Non-inferiority trial to evaluate the Immunogenicity and Safety of Tri Fluvac, a Seasonal Trivalent Inactivated Split Virion Influenza Vaccine, in Healthy Thai Subjects Aged 18 – 49 Years.						
Protocol #:	GPO Tri Fluvac Vaccine Phase II/III						
Description of Study Design:	This is a phase II/III, non-inferiority double-blinded, randomized, controlled trial of immunogenicity and safety with two groups of participants who will received a seasonal trivalent split, inactivated influenza vaccine (A/H1N1; A/H3N2 and B) or an active comparator (licensed influenza vaccine).						
	A total of about 945 healthy Thai male and female adult volunteers 18 through 49 years of age; 630 participants will be randomized to receive the GPO Tri Fluvac and 315 will receive an active comparator (a 2:1 ratio) (inclusion of ~7% lost to follow-up).						
	Safety will be assessed for all participants through Day 90 after vaccination. Immunogenicity will be assessed in serum samples obtained at baseline and 21 days after vaccination in a subset of at least 586 individuals randomized to study vaccine and 293 active comparator vaccine recipients.						
Study Hypothesis:	Immunogenicity: A single dose of the GPO seasonal trivalent split, inactivated influenza vaccine will induce immune responses measured by HI assay to each of the three vaccine antigens and will be non-inferior to active licensed comparator vaccine.						
	Safety : A single dose of the GPO seasonal trivalent split, inactivated influenza vaccine will be safe and well tolerated in adults 18 to 49 years of age.						
Study	Primary objective						
Objectives.	Immunogenicity:						
	To evaluate the immunological non-inferiority seroconversion rate (using HI assay) and Geometric Mean Titre (GMT) of the GPO seasonal trivalent split, inactivated influenza vaccine compared to active comparator vaccine for each of the three vaccine antigens, three weeks after immunization (Day 21) and at the end of follow-up period (Day 90).						
	Safety:						
	To evaluate the safety profile of a single intramuscular dose of the GPO seasonal trivalent split, inactivated influenza vaccine in adults 18 to 49 years of age.						
	To compare the solicited symptoms, AE and SAE between subjects who will receive GPO trivalent split, inactivated influenza vaccine and those who will receive active comparator vaccine.						

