# 2.6 Potential risks and benefits of the study

The investigational vaccine may cause severe allergic reactions (e.g. anaphylaxis) when administered to anyone with known history of severe allergic reactions to egg proteins (eggs or egg products), or to any component of the vaccine (e.g. gentamicin, thimerosal). Some subjects may experience systemic reactions such as increased fatigue, headache, dizziness/vertigo), fever, runny nose, pharyngitis, cough, arthralgia, myalgia, nausea/vomiting. As usual, these symptoms go away by themselves within 1-3 days. In extremely rare cases of high individual sensitivity allergic reactions could be observed. There is a small possibility that inactivated influenza vaccine could be associated with Guillain-Barré Syndrome (GBS), no more than 1 or 2 cases per million people vaccinated. This is much lower than the risk of severe complications from flu, which can be prevented by flu vaccine (http://www.cdc.gov/vaccines/hcp/vis/vis-statements/flu.html).

The efficacy of this Tri Fluvac vaccine has not been evaluated before. However, the virus compositions included in the vaccine correspond to 2017 strains recommended by WHO for Southern Hemisphere.

Collection of blood samples through venipuncture may also cause subjects some discomfort or pain, redness, selling and/or hardness at the puncture site. By participating in this study, subjects will be screened by qualified clinicians for health status and through laboratory testing. This screening will be free of cost to the subject and may provide important information to the subject on the subject's health status.

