## 4.2 Rationale of Study Design

Inactivated influenza vaccine has a well-established safety profile having been prescribed to millions of individuals globally, including children, the elderly, pregnant women, and individuals with chronic disease and immune suppression. Inactivated influenza vaccine also has well established international guidance including quantification of antigen, manufacturing, testing specifications for final bulk and final products, and requirements for national control authorities [30]. Because of predictable immunogenicity, dose finding studies of traditional, non-adjuvanted inactivated influenza are often not required. Furthermore, an immunogenicity study in lieu of an efficacy study as measured by HI (the surrogate endpoint) are common practice for inactivated influenza vaccines.

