Appendix 06: Listing of Adverse Event	. 78
Appendix 07: Listing of Illness like Influenza (ILI)	. 78
Appendix 08: Listing of Concomitant Medication	. 79
Appendix 09: List of HAI Assay (Flu A H1 Antigen)	. 80
Appendix 10: List of HAI Assay (Flu A H3 Antigen)	. 80

Study Synopsis

Title: A Phase II/III Double Blinded, Randomized, Controlled, Non-inferiority trial to evaluate the Immunogenicity and Safety of Tri Fluvac, a Seasonal Trivalent Inactivated split virion Influenza vaccine, in healthy Thai subjects aged 18 – 49 years.

Protocol #: GPO Tri Fluvac Vaccine Phase II/III

Description of Study Design:

This is a phase II/III, non-inferiority double-blinded, randomized, controlled trial of immunogenicity, safety and preliminary efficacy with two groups of participants who will received a seasonal trivalent split, inactivated influenza vaccine (A/H1N1; A/H3N2 and B) or an active comparator (licensed influenza vaccine).

A total of about 945 healthy Thai male and female adult volunteers 18 through 49 years of age; 630 participants will be randomized to receive vaccine and 315 will receive an active comparator (a 2:1 ratio) (inclusion of \sim 7% lost to follow-up).

Safety will be assessed for all participants through Day 90 after vaccination. Immunogenicity will be assessed in serum samples obtained at baseline and 21 days after vaccination in a subset of at least 630 individuals randomized to study vaccine and 315 active comparator vaccine recipients.

Study Hypothesis:

Immunogenicity: A single dose of the GPO seasonal trivalent split, inactivated influenza vaccine will induce immune responses measured by HI assay to each of the three vaccine antigens and will be non-inferior to active licensed comparator vaccine.

Safety: A single dose of the GPO seasonal trivalent split, inactivated influenza vaccine will be safe and well tolerated in adults 18 to 49 years of age.

Study Objectives:

Primary objective

Immunogenicity:

To evaluate the immunological non-inferiority seroconversion rate (using HI assay) and Geometric Mean Titre (GMT) of the GPO seasonal trivalent split, inactivated influenza vaccine compared to active comparator vaccine for each of the three vaccine antigens, three weeks after immunization (Day 21) and at the end of follow up period (Day 90).

Safety:

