*ILI-illness like influenza

TREF 2.6: Summary Number of Subjects with Illness like Influenza (ILI) by GPO Tri fluvac and Active Comparator Group

	Tri fluvac (N = xx)	Comparator (N = xx)	
Illness like Influenza (ILI)			_
Yes			
No			
p-value = xxx			

Note: This table will be showed number of subjects with and without ILI.

	Tri fluvac	Comparator
	(N = xx)*	$(N = xx)^*$
Temperature (°C)		
n		
Mean(SD)		
Median		
Min, Max		
P- value =		
Pulse (Beats per minute)		
n		
Mean(SD)		
Median		
Min, Max		
P- value =		
Blood Pressure		
Systolic (mmHg)		
n		
Mean(SD)		
Median		
Min, Max		
P- value =		
Diastolic		
n		
Mean(SD)		
Median		
Min, Max		
P- value =		

TREF 2.7: Vital Sign of Illness like Influenza (ILI) by GPO Tri fluvac and Active Comparator Group

Note: - Vital sign will be compared between GPO Tri fluvac and Active Comparator.

- * Number of illness like influenza (ILI) events

- Only subject with of illness like influenza (ILI) will be considered for this table.

		Tri fluvac (N = xx)*	Comparator (N = xx)*
HEENT, n (%)			
Normal		xx(xx.xx)	xx(xx.xx)
Abnormal		xx(xx.xx)	xx(xx.xx)
	P- value = x.xxxx		
Lungs, n (%)			
Normal			
Abnormal			
	P- value =		
Cardiovascular, n	(%)		
Normal			
Abnormal			
	P- value =		
Gastrointestinal, n	(%)		
Normal			
Abnormal			
	P- value =		
Musculoskeletal, n	(%)		
Normal			
Abnormal			
	P- value =		
Skin, n (%)			
Normal			
Abnormal			
	P- value =		
Neurologic, n (%)			
Normal			
Abnormal			
	P- value =		

TREF 2.8: Physical Examination of Illness like Influenza (ILI) Events by GPO Tri fluvac and Active Comparator Group

Note: - Physical examination will be compared between GPO Tri fluvac and Active Comparator.

- * Number of illness like influenza (ILI) events

- Only subject with of illness like influenza (ILI) will be considered for this table.

	Tri fluvac (N = xx)*	Comparator (N = xx)*
Nasal Swab Test Result		
Not done	xx(xx.xx)	xx(xx.xx)
Inconclusive	xx(xx.xx)	xx(xx.xx)
Influenza A		
Positive	xx(xx.xx)	xx(xx.xx)
Negative	xx(xx.xx)	xx(xx.xx)
P-value = x.xxxx		
Influenza B		
Positive	xx(xx.xx)	xx(xx.xx)
Negative	xx(xx.xx)	xx(xx.xx)
P-value = x.xxxx		
Throat Swab Test Result		
Not done	xx(xx.xx)	xx(xx.xx)
Inconclusive	xx(xx.xx)	XX(XX.XX)
Influenza A		
Positive	xx(xx.xx)	XX(XX.XX)
Negative	xx(xx.xx)	XX(XX.XX)
P-value = x.xxxx		
Influenza B		
Positive	xx(xx.xx)	XX(XX.XX)
Negative	xx(xx.xx)	XX(XX.XX)
P- value = x.xxxx		
Conclusion of RT-PCR		
Influenza A H1		
Influenza A H3		
Influenza A H5		
Influenza A unspecified		

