Influenza B		
Inconclusive test results		
Influenza not detected		
Other		

TREF 2.9: Summary RT- PCR Test for II	lness like Influenza	(ILI) Events by GPO) Tri fluvac and
Active Comparator Group			

Other.....

	Tri fluvac	Comparator
	$(N = xx)^*$	$(N = XX)^*$
Final Diagnosis		
Influenza		
ILI		

TREF 2.9: Summary RT- PCR Test for Illness like Influenza (ILI) Events by GPO Tri fluvac and Active Comparator Group (Continue)

Note: - Only subject with of illness like influenza (ILI) will be considered for this table.

- * Number of illness like influenza (ILI) events

P-value = x.xxxx

- Test result will be compared between GPO Tri fluvac and Active Comparator.

3. Post Immunization Reaction

Temperature Grading

- TREF 3.1 Comparison of Temperature Grading at Follow up Visit by GPO Tri Fluvac and Active Comparator Group
- TREF 3.2 Comparison of Temperature Grading at Post Immunization by GPO Tri Fluvac and Active Comparator Group

Vital Sign

TREF 3.3: Vital Sign by GPO Tri Fluvac and Active Comparator Group

Physical Examination

TREF 3.4: Physical Examination by GPO Tri Fluvac and Active Comparator Group

Post Immunization Reaction

Local Reaction Post Immunization

- TREF 3.5 Comparison of Maximum Grade of Local Reaction at Post Immunization by GPO Tri Fluvac and Active Comparator Group
- TREF 3.6 Comparison of Local Reaction at Post Immunization each Follow up Time by GPO Tri Fluvac and Active Comparator Group
- TREF 3.7 Comparison of Maximum Grade of Local Reaction by Symptom at Post Immunization by GPO Tri Fluvac and Active Comparator Group
- TREF 3.8: Summary Number of Local Reaction Days by Symptom at Post Immunization
- TREF 3.9: Summary Number of Local Reaction by Symptom at Post Immunization

Systemic Reaction Post Immunization

- TREF 3.10 Comparison of Maximum Grade of Systemic Reaction at Post Immunization by GPO Tri Fluvac and Active Comparator Group
- TREF 3.11 Comparison of Systemic Reaction at Post Immunization each Follow up Visit by GPO Tri Fluvac and Active Comparator Group
- TREF 3.12 Comparison of Maximum Grade of Systemic Reaction by Symptom at Post Immunization by GPO Tri Fluvac and Active Comparator Group
- TREF 3.13: Summary Number of Systemic Reaction Days by Symptom at Post Immunization
- TREF 3.14: Summary Number of Systemic Reaction by Symptom at Post Immunization

	Tri fluvac	Comparator
Follow up Visit	(N = xx)	(N = xx)
•	n (%)	n (%)
Day 0		
- Grade 0	xx(xx.xx)	xx(xx.xx)
- Grade 1	xx(xx.xx)	xx(xx.xx)

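### The SAP synopsis adds preliminary efficacy to the trial's purpose, which nothing else in either document supports, and its ILI and RT-PCR tables print p-values that could be read as efficacy evidence

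*SAP*

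**What the plan says.** The SAP's Study Synopsis, under Description of Study Design, describes a trial of "immunogenicity, safety and preliminary efficacy with two groups of participants". The corresponding sentence in the protocol (section 1, Protocol Summary) reads "controlled trial of immunogenicity and safety with two groups of participants", and protocol section 4.1 likewise names only safety and immunogenicity. The titles of both documents agree with the protocol.

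On efficacy, protocol section 2.6 states "The efficacy of this Tri Fluvac vaccine has not been evaluated before". Section 4.2 says that "an immunogenicity study in lieu of an efficacy study as measured by HI (the surrogate endpoint) are common practice" for inactivated influenza vaccines.

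The protocol does plan to collect influenza-like illness (ILI) reports and swabs for RT-PCR (section 4.1, Table 2, sections 7.4.3, 7.6 and 8.12). It gives no ILI case definition and no analysis of these data, and its Exploratory Analysis section (11.3.3) is empty.

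The SAP provides four ILI tables under its Safety Assessment heading:
- **TREF 2.6:** ILI yes/no by arm, with a p-value. Its note reads "This table will be showed number of subjects with and without ILI".
- **TREF 2.7 and 2.8:** vital signs and physical examination in ILI, with p-values.
- **TREF 2.9:** RT-PCR results, with p-values for influenza A, influenza B and final diagnosis. Its note reads "Test result will be compared between GPO Tri fluvac and Active Comparator".

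The footnotes to TREF 2.7, 2.8 and 2.9 define N as the number of ILI events and limit the tables to subjects with ILI.

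**The concern.** The SAP states a purpose that the protocol does not have, and its table shells include between-arm tests on clinical influenza outcomes. No hypothesis, margin or sample size stands behind those tests. A non-significant p-value for ILI or confirmed influenza, reported from a trial whose SAP names preliminary efficacy as a purpose, could be quoted as a sign that the two vaccines protect equally well. The trial was not built to show that.

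There are two further problems. TREF 2.7-2.9 compare arms only among ILI events, so they condition on something that happens after randomisation and are not randomised comparisons. In addition, protocol section 11.4 rules out statistical testing of unsolicited adverse events. The SAP links ILI to adverse events (an ILI column in TREF 2.5 and a related-AE field in Appendix 07), so if ILI is recorded as an unsolicited event, the ILI tests conflict with that rule.

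**Working it through.** **1. What the sample size was built for.** Protocol section 11.2 bases N on seroconversion non-inferiority for H3: rate 0.535 in both arms, margin 0.10, one-sided alpha 0.025, power 80%, ratio 2:1.

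n_S = (1.960 + 0.842)² × 0.535 × 0.465 × (1 + 1/2) / 0.10² ≈ 293, and n_T = 586, total 879.

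Dividing by 0.93 gives 315.05 and 630.1, which the protocol states as 315 + 630 = 945. The plan's figure is reproduced. The GMT calculation needs only 354. Clinical influenza does not enter either calculation.

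**2. Absolute efficacy.** Both arms receive a vaccine against the same three strains (protocol section 1, descriptions of the agent and the comparator). With no unvaccinated arm, absolute efficacy cannot be estimated.

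**3. Expected influenza cases.** Inputs: 945 participants, 90 days of follow-up (section 4.1), and an annual adult attack rate of 5-10% (section 2.2). Assumption: incidence is spread evenly over the year.

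- No protection: 945 × 0.05 × 90/365 = 11.7, and 945 × 0.10 × 90/365 = 23.3.
- Protection of 50% in both arms (an assumption; the documents give no figure): 5.8 to 11.7.

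**4. Precision of the risk ratio.** At equal risk and 2:1 allocation, 12 cases fall as 8 versus 4, and 6 cases as 4 versus 2. The 95% CI factor is exp[1.96 × √(1/a + 1/b − 1/630 − 1/315)].

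| Cases (630 vs 315) | Factor | 95% CI for risk ratio of 1 |
|---|---|---|
| 8 vs 4 | 3.30 | 0.30 to 3.30 |
| 4 vs 2 | 5.43 | 0.18 to 5.43 |

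**5. Power for a doubling.** Fisher's exact test, 630 versus 315, two-sided 0.05, with the Tri Fluvac risk twice the comparator risk. The ranges correspond to annual rates of 5% to 10%.

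| Rate assumption | Protection in comparator arm | Comparator risk | Power |
|---|---|---|---|
| Pro-rated to 90/365 | none | 1.23%-2.47% | 20%-41% |
| Pro-rated to 90/365 | 50% (assumed) | 0.62%-1.23% | 7%-20% |
| Whole annual rate within 90 days (upper bound) | 50% (assumed) | 2.5%-5% | 41%-77% |
| Whole annual rate within 90 days (upper bound) | none | 5%-10% | 77%-98% |

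Under the pro-rated rates, a doubling would more likely than not be missed. If a season's worth of influenza fell inside the follow-up, that would no longer hold throughout.

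**6. Scope of these figures.** They concern influenza cases. TREF 2.6 counts all ILI, for which the documents give no rate, so no power can be stated for that table.

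**The case against.** The strongest reply is that this is a stray phrase. The SAP's title, hypotheses, objectives and endpoints cover HI response and safety only, TREF 2.6-2.9 already stand under Safety Assessment, and the SAP nowhere calls them efficacy analyses. ILI and RT-PCR collection is planned in the protocol, so the SAP adds only the label and the tests. The SAP also prints p-values almost everywhere, baseline tables included. And the statement in section 4.2 about studying immunogenicity in place of efficacy is a remark on general practice. All of this stands, and it makes the point minor. It does not remove the fact that the SAP states a purpose nothing in the plan serves, or that three of the four tables test within a post-randomisation subset.

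A reader might infer stronger versions, which the documents do not support:

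- **A non-significant result is nearly certain whatever the vaccines do.** Power is low at the pro-rated rates, but it is not negligible in every scenario in step 5.
- **A threefold difference in protection could not be excluded.** The interval is for the ratio of risks, which is a different quantity from protection.
- **No efficacy quantity at all can be estimated.** Relative efficacy can be estimated, but imprecisely.
- **ILI first reported at Day 60 or Day 90 goes untested.** Section 7.6 asks participants to present within 48 hours, but section 4.1 calls for a swab in those reporting ILI without a time limit, and Table 2 allows RT-PCR at both contacts.
- **Early vaccine reactions count as ILI.** No counting rule says so, and sections 8.2 and 8.5 keep reactions starting in the first three days as solicited events. For the same reason, the documents give no basis for splitting ILI at a particular day of onset.

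**Conclusion.** The point holds as a minor inconsistency. The SAP's reference to preliminary efficacy has no counterpart in the protocol and no supporting objective, endpoint, hypothesis, margin or sample size in either document. Absolute efficacy is out of reach by design. For relative efficacy, a plausible count of 8 versus 4 influenza cases leaves a risk ratio anywhere from about 0.3 to 3.3, so a non-significant p-value is likely even if influenza risk doubled and says nothing about similarity. This rests on spreading the protocol's annual attack rate evenly over the year and, for the lower counts, on an assumed 50% protection. Section 2.2 describes a peak around the rainy season, which could raise the counts.

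The conflict with section 11.4 is conditional on ILI being recorded as an unsolicited adverse event. The primary non-inferiority conclusion, its sample size and its error rate are untouched. What changes is how the ILI and influenza results are reported and what may be concluded from them.

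**What to change.** 1. Delete the reference to preliminary efficacy from the SAP synopsis, so that it matches protocol sections 1 and 4.1.
2. Mark TREF 2.6-2.9 as descriptive and remove their p-values.
3. Report ILI and RT-PCR-confirmed influenza as the number and percentage of vaccinated participants in each arm, with exact 95% CIs. Tables describing ILI events may remain as listings or summaries without between-arm tests.
4. State in the SAP that no efficacy inference will be drawn from these data.

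The cost is a few lines of SAP wording and edits to four table shells. No new data are needed. The sponsor gives up only an efficacy statement that the design could not support.
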